5.4.6 Debriefing

Explain whether and how subjects will be debriefed after participation in the study. If subjects will not be debriefed, provide a justification for not doing so. Add any debriefing materials to the study in CATS IRB.

N/A

5.5 Informed consent will not be obtained – request to completely waive the informed consent requirement

Review “HRP-410-Checklist -Waiver or Alteration of Consent Process” to ensure that you have provided sufficient information.

5.5.1 Indicate why the research could not practicably be carried out without the waiver of consent

N/A

5.5.2 Describe why the research involves no more than minimal risk to subjects.

N/A

5.5.3 Describe why the alteration/omission will not adversely affect the rights and welfare of subjects.

N/A

5.5.4 If the research involves using identifiable private information or identifiable biospecimens, describe why the research could not be practicably be carried out without using such information or biospecimens in an identifiable format.

N/A

5.5.5 Additional pertinent information after participation

Explain if subjects will be provided with additional pertinent information after participation. If not applicable, indicate “not applicable.”

N/A

5.6 Consent – Other Considerations

5.6.1 Non-English-Speaking Subjects

Indicate what language(s) other than English are understood by prospective subjects or representatives.

If subjects who do not speak English will be enrolled, describe the process to ensure that the oral and written information provided to those subjects will be in that language. Indicate the language that will be used by those obtaining consent.

Indicate whether the consent process will be documented in writing with the long form of the consent documentation or with the short form of the consent documentation. Review “HRP-091 –SOP- Written Documentation of Consent” and “HRP-103 -Investigator Manual” to ensure that you have provided sufficient information.

N/A

5.6.2 Cognitively Impaired Adults

Refer “HRP-417 -CHECKLIST- Cognitively Impaired Adults” for information about research involving cognitively impaired adults as subjects.

5.6.2.1 Capability of Providing Consent

Describe the process to determine whether an individual is capable of consent.

N/A

5.6.2.2 Adults Unable to Consent

Describe whether and how informed consent will be obtained from the legally authorized representative. Describe who will be allowed to provide informed consent. Describe the process used to determine these individual's authority to consent to research.

For research conducted in the state of Pennsylvania, review “HRP-013 -SOP- Legally Authorized Representatives, Children and Guardians” to be aware of which individuals in the state of Pennsylvania meet the definition of “legally authorized representative.”

For research conducted outside of the state of Pennsylvania, provide information that describes which individuals are authorized under applicable law to consent on behalf of a prospective subject to their participation in the procedure(s) involved in this research. One method of obtaining this information is to have a legal counsel or authority review your protocol along with the definition of “children” in “HRP-013 -SOP- Legally Authorized Representatives, Children, and Guardians.”

N/A

5.6.2.3 Assent of Adults Unable to Consent

Describe the process for assent of the subjects. Indicate whether assent will be required of all, some or none of the subjects. If some, indicate which subjects will be required to assent and which will not.

If assent will not be obtained from some or all subjects, provide an explanation of why not.

Describe whether assent of the subjects will be documented and the process to document assent. The IRB allows the person obtaining assent to document assent on the consent document and does not routinely require assent documents and does not routinely require subjects to sign assent documents.

N/A

5.6.3 Subjects who are not yet adults (infants, children, teenagers)

5.6.3.1 Parental Permission

Describe whether and how parental permission will be obtained. If permission will be obtained from individuals other than parents, describe who will be allowed to provide permission. Describe the process used to determine these individual's authority to consent to each child's general medical care.

For research conducted in the state of Pennsylvania, review "HRP-013-SOP- Legally Authorized Representatives, Children and Guardians" to be aware of which individuals in the state of Pennsylvania meet the definition of "children."

For research conducted outside of the state of Pennsylvania, provide information that describes which persons have not attained the legal age for consent to treatments or procedures involved in the research, under the applicable law of the jurisdiction in which research will be conducted. One method of obtaining this information is to have a legal counsel or authority review your protocol along with the definition of "children" in "HRP-013-SOP- Legally Authorized Representatives, Children, and Guardians."

N/A

5.6.3.2 Assent of subjects who are not yet adults

Indicate whether assent will be obtained from all, some, or none of the children. If assent will be obtained from some children, indicate which children will be required to assent. When assent of children is obtained describe whether and how it will be documented.

N/A

****Site Congruency: Is the information provided in the above section (Consent Process and Documentation) consistent across all relying sites in this research?**

Yes

No - Identify the sites that have dissimilar procedures: *[This field should solely identify the site. Dissimilar procedures across sites should be identified in the SITE workspace via HRP-XXX – R2S Site Plan]*

6.0 HIPAA Research Authorization and/or Waiver or Alteration of Authorization

This section is about the access, use or disclosure of Protected Health Information (PHI). PHI is individually identifiable health information (i.e., health information containing one or more 18 identifiers) that is transmitted or maintained in any form or medium by a Covered Entity or its Business Associate. A Covered Entity is a health plan, a health care clearinghouse or health care provider who transmits health information in electronic form. See "HRP-103 -Investigator Manual" for a list of the 18 identifiers.

If requesting a waiver/alteration of HIPAA authorization, complete sections 6.2 and 6.3 in addition to section 6.1. The Privacy Rule permits waivers (or alterations) of authorization if the research meets certain conditions. Include only information that will be accessed with the waiver/alteration.

[Do not type here]

6.1 Authorization and/or Waiver or Alteration of Authorization for the Uses and Disclosures of PHI

Check all that apply:

- Not applicable, no identifiable protected health information (PHI) is accessed, used or disclosed in this study. [Mark all parts of sections 6.2 and 6.3 as not applicable]**
- Authorization will be obtained and documented as part of the consent process. [If this is the only box checked, mark sections 6.2 and 6.3 as not applicable]**
- Partial waiver is requested for recruitment purposes only (Check this box if patients' medical records will be accessed to determine eligibility before consent/authorization has been obtained). [Complete all parts of sections 6.2 and 6.3]**

- Full waiver is requested for entire research study (e.g., medical record review studies).**
[Complete all parts of sections 6.2 and 6.3]
- Alteration is requested to waive requirement for written documentation of authorization (verbal authorization will be obtained).** *[Complete all parts of sections 6.2 and 6.3]*

6.2 Waiver or Alteration of Authorization for the Uses and Disclosures of PHI

6.2.1 Access, use or disclosure of PHI representing no more than a minimal risk to the privacy of the individual

6.2.1.1 Plan to protect PHI from improper use or disclosure

Include the following statement as written – DO NOT ALTER OR DELETE unless this section is not applicable because the research does not involve a waiver of authorization. **If the section is not applicable, remove the statement and indicate as not applicable.**

Information is included in the “Confidentiality, Privacy and Data Management” section of this protocol or in “HRP-598 – Research Data Plan Review Form”.

6.2.1.2 Plan to destroy identifiers or a justification for retaining identifiers

Describe the plan to destroy the identifiers at the earliest opportunity consistent with the conduct of the research. Include when and how identifiers will be destroyed. If identifiers will be retained, provide the legal, health or research justification for retaining the identifiers.

Authorization for Collection of Health Information: Authorization for the Fitbit (actigraphy), Fitbit Scale (weight), blood pressure monitor, and carbon monoxide monitor will be obtained and documented during consent procedures. After consent is obtained, NPF visiting nurses will provide women with information on how to use the devices. Data from the Fitbit and Fitbit Scale will connect to a smartphone app on the women’s phone; the study team will not have access the data and will not be connected to identifying information. However, participants may verbally share data from these devices with nurses. Nurses will review data from blood pressure monitor using a paper tracking log provided by the study team and data from the carbon monoxide monitor will be reviewed with participants at study visits. This data will not be connected to identifying information.

6.2.2 Explanation for why the research could not practicably be conducted without access to and use of PHI

Provide an explanation for why the research could not practicably be conducted without access to and use of PHI.

Authorization for Collection of Health Information: Authorization for the Fitbit (actigraphy), Fitbit Scale (weight), blood pressure monitor, and carbon monoxide monitor will be obtained and documented during consent procedures. Given the that a primary goal of this pilot is to test the feasibility of using commercial devices to collect these data, study goals could not be met.

6.2.3 Explanation for why the research could not practically be conducted without the waiver or alteration of authorization

Provide an explanation for why the research could not practically be conducted without the waiver or alteration of authorization.

Given the that a primary goal of this pilot is to test the feasibility of using commercial devices to collect these data, study goals could not be met.

6.3 Waiver or alteration of authorization statements of agreement

By submitting this study for review with a waiver of authorization, you agree to the following statement – DO NOT ALTER OR DELETE unless this section is not applicable because the research does not involve a waiver or alteration of authorization. **If the section is not applicable, remove the statement and indicate as not applicable.**

Protected health information obtained as part of this research will not be reused or disclosed to any other person or entity, except as required by law, for authorized oversight of the research study, or for other permitted uses and disclosures according to federal regulations.

The research team will collect only information essential to the study and in accord with the 'Minimum Necessary' standard (information reasonably necessary to accomplish the objectives of the research) per federal regulations.

Access to the information will be limited, to the greatest extent possible, within the research team. All disclosures or releases of identifiable information granted under this waiver will be accounted for and documented.

****Site Congruency: Is the information provided in the above section (HIPAA Research Authorization and/or Waiver or Alteration of Authorization) consistent across all relying sites in this research?**

Yes

No – Identify the sites that have dissimilar procedures: *[This field should solely identify the site.*

Dissimilar procedures across sites should be identified in the SITE workspace via HRP-XXX – R2S Site Plan]
[Type protocol text here]

7.0 Study Design and Procedures

Data collection materials that will be seen or used by subjects in your study must be uploaded to CATS IRB (<http://irb.psu.edu>). **DO NOT** include any actual data collection materials in this protocol (e.g., actual survey or interview questions). Remove any section that does not apply (research not involving drug/device).

[Do not type here]

7.1 Study Design

Describe and explain the study design.

This is a single arm study in which women who are pregnant and participating in the NFP program will be recruited into a study of traditional NFP care with enhanced care focusing on improving CVH throughout the pregnancy and up to 6 months postpartum.

7.2 Study Procedures

Provide a step by step description of all research procedures being conducted (broken down by visit, if applicable) including such information as below (where and when applicable); describe the following:

- HOW: (e.g., data collection via interviews, focus groups, forms such as surveys and questionnaires, medical/school records, audio/video/digital recordings, photographs, EKG procedures, MRI, mobile

- devices such as electronic tablets/cell phones, observations, collection of specimens, experimental drug/device testing, manipulation of behavior/use of deception, computer games, etc.)
- WHERE: (e.g., classrooms, labs, internet/online, places of business, medical settings, public spaces, etc.)

Intervention Overview. Our pilot CVH intervention will be delivered by NFP visiting nurses starting as early as NFP program enrollment in the first trimester after confirmation of a viable pregnancy and no later than the 28th week of pregnancy and will continue up to 6 months postpartum. The visit schedule will be consistent with the NFP program visit structure to deliver intervention content at regularly scheduled visits that are typically 60 minutes long (weekly visits for the first month following enrollment followed by twice monthly visits until delivery).

The pilot intervention will include a behavioral component aimed at reducing sedentary behaviors as well as utilizing a technology/monitoring component. We will monitor all mothers with a wrist-worn actigraphy device (FitBit) to record activity and sleep, weight scale (Fitbit Scale), intermittent home ambulatory blood pressure self-monitoring (HBPM), and carbon monoxide monitoring administered by the NFP visiting nurse. Carbon monoxide monitoring is part of an attempt to reduce the use of nicotine-containing products. Monitoring with digital devices is discussed below and in the digital device section which follows a description of the interventions. However, the participant will have access to the digital data on the device through smartphone or computer apps to reinforce desired behaviors.

Implementation. Our behavior change strategies will involve interactive, skill-based intervention will be delivered in-person by NFP visiting nurses and include health coaching to modify short- and long-term health behaviors, electronic and print resources, and referrals to community resources (e.g., smoking cessation 1-800-QUIT NOW). Curricula are informed by our ongoing and prior work as well as modules developed by the Diabetes Prevention Program (DPP) and freely available. NFP home visiting nurses will document information related to session implementation (e.g., length of visit, quality of delivery, participant engagement).

Lifestyle Behaviors. Includes self-assessment of lifestyle behaviors, self-monitoring with the digital devices, monitoring tools, reflection, written materials, situated learning, and guided goal setting and action planning to meet behavior change goals. Activity will be monitored continuously via a wrist-worn actigraphy device (Fitbit) and data on physical activity and sleep reviewed with the visiting nurse at each visit. The Fitbit is a low-burden, continuous assessment tool. The Fitbit will be able to provide continuous heart rate, temperature and activity monitoring. Reducing sedentary activity and setting activity goals will be tailored to the patient's baseline condition, stage and complications of pregnancy and the puerperal state. Aside from self-monitoring, topics from the DPP reducing sedentary behavior will be reinforced. Specifically, we will utilize the DPP-GLB physical activity modules to address activity. They have two modules specifically focused on sedentary behavior and less sitting time.

Impact of lifestyle behaviors. Home visitors will discuss associated risks, treatment, and surveillance of pertinent pregnancy conditions including prevention of hypertension as well as tobacco cessation when applicable.

Sedentary behaviors and Physical activity. Participants will receive information about the importance of being active and how to adjust their lifestyle to accommodate more activity with encouragement to exercise, working toward two daily goals: 1) reducing sedentary time and 2) aiming for 30 minutes moderate physical activity daily. Additionally, we will focus on increasing the level of activity after delivery to achieve moderate intensity of activity.

Sedentary behavior is a modifiable risk factor for CVH.^{210,211} Participants will be guided on reducing sedentary behaviors including screen time (i.e., television, computer devices, mobile connectivity) to meet physical activity guidelines. We will utilize the DPP modules and scripting to reduce sedentary activity as noted above (see uploaded intervention documents). The goal will be to limit screen-based sitting time (e.g. TV or computer) outside of work to less than 2 hours per day and break up long continuous bouts of sitting (defined as sedentary > 2 hours) with periods of movement (standing up,

stretching, walking around). Participants will have access to feedback related to sedentary behavior via an app downloaded on their personal cell phone. Materials will emphasize the goal of reduced sedentary activity as noted above and provide guidance for increased physical activity as determined by the patient's recovery from the mode of delivery by the nurse. For physical activity, an example goal would be to specify a certain number of steps in a limited time to increase activity, for instance 1,000 steps in 10 minutes, 2,000 steps in 20 minutes, 3,000 steps in 30 minutes. Sedentary participants will be given graduated regimens to achieve these goals. These goals will be individualized rather than relying on set goals of weekly increases. We will utilize modules developed by the DPP to introduce increased aerobic activity (see supplements and DPP manual). Ultimately the participant in the puerperium period should reach 150 minutes per week of exercise. Education will include exercise definitions, guidelines, safety, myths, goals, overcoming barriers, and practical strategies to increase daily activity level.

Nicotine and Tobacco Cessation. Nicotine use, and particularly cigarette smoking is a key modifiable risk factor for CVH, in addition to numerous other maternal-child health indicators. During the pilot, we will aim to recruit at least 5 women with nicotine use in the past 3 months (cigarette, cigar, hookah, chewing tobacco, e-cigarettes, patch) into the study to pilot enhanced intervention to reduce nicotine use (and particularly cigarette smoking). Cigarette and e-cigarette use will be the most common sources of nicotine exposure, and cigarette smoking likely the most harmful. Carbon monoxide screening will be used throughout on all patients to document new exposure or recidivism, which would trigger enrollment into an enhanced intervention. We will use the Micro+™ baby Smokerlyzer® from Covita. This monitor can be used during pregnancy and postpartum. It measures three relevant feedback parameters to the patient: PPM – CO in the lungs, %COHb – CO in the blood and %FetalCOHb – fetus CO level. Baseline assessment will record ever use of any tobacco/nicotine product and from that point and at subsequent visits will focus on assessment of the average frequency of use per day over the previous 7 days. Non-smoking will be reinforced, and smokers will be provided with evidence-based education and motivational interviewing counseling based on the existing NFP protocols. In addition, as soon as women who have used a nicotine product in the previous 3 months agree, they will be assisted to call and enroll with the national smoking cessation Quitline where they will receive pro-active callback counseling, written materials, and other intervention modalities (e.g. texting and online support). These interventions will be repeated as required throughout the trial using a chronic care model rather than a single intervention model.¹²⁴ Nicotine replacement and/or medication may be provided by the Quitline according to their standard protocols for pregnant women, requiring written approval from the woman's provider, prescribed in order to achieve smoking cessation or reduction. Compliance will be monitored with carbon monoxide monitoring. We have developed a protocol and script for delivering this intervention to achieve smoking cessation (see uploaded intervention documents).

We next include a summary of the study visit table with study specific parameters on mothers only for this pilot (NOTE as per above NFP visits will be more frequent).

Table 1. Study Visit Table

CONSTRUCT	MEASURE	Prenatal and/or Postpartum		
		Study entry (V1)	+ 1 month (V2)	+2 months (V3)
Smoking status	National Adult Smoking Survey questions	S	S	S
Home Blood Pressure Monitoring (HBPM)	Systolic/diastolic blood pressure three times a week; nurse review results at each visit and provide referrals for high readings	C / N	C / N	C / N
Carbon Monoxide (CO) Monitoring	CO monitoring will take place to monitor for smoke exposure, faulty ventilation, etc.	N	N	N
Physical Activity	Sedentary time, steps, intensity, hours/week monitored by actigraphy device	C	C	C
Demographic/baseline characteristics	Developed for ENRICH	S		S
Satisfaction	Developed for ENRICH			S

S=survey; C= client self-monitoring; N= nurse administered

MATERNAL MODIFIED AMERICAN HEART ASSOCIATION HEALTH INDICATORS

Smoking. Maternal smoking status will be assessed at baseline using items from the National Adult Smoking Survey including: “Have you ever smoked a cigarette, even one or two puffs?”; “About how many cigarettes have you smoked in your entire life?”; “During the past 30 days, on how many days did you smoke cigarettes?”; “When was the last time you smoked a cigarette, even one or two puffs?”; and “During the past 30 days, on the days you smoked, about how many cigarettes did you smoke per day?” A script is provided for the NFP nurse to administer this intervention. This will be repeated at the designated time points in Table 1 among known smokers only.

DIGITAL DEVICE MONITORING

Our plan will be to use digital devices that can be accessed through apps on participant smart phones. The participants will have immediate access to the data from the Fitbit and Fitbit Scale, through Bluetooth links to their smartphone or computer. Research data will not be collected from these devices (i.e., the research team will not have access to data from the Fitbit or Fitbit Scale). However, NFP home visiting nurse will answer any questions related to physical activity and weight as standard care. The research team will ask participants to document readings from the blood pressure monitor on a study tracking log. This log will be reviewed by the NFP visiting nurse at each home visit and referral provided for high readings as appropriate (details below).

Physical Activity Monitoring. We will use a commercially available wrist-worn device, the Fitbit Charge 5, to monitor physical activity. This device has a long battery life of 7 days and is compatible with a wide variety of devices and operating systems and can differentiate type and duration of activity.

Weight Monitoring: We will use a commercially available digital scale, the Fitbit Aria Scale, to monitor participant weight. This device has a long battery life and is compatible with a wide variety of devices (including the Fitbit) and operating systems.

Home Blood Pressure Monitoring (HBPM). We will utilize the devices and methodology (including apps and central database) utilized in the BUMP 1 and 2 trials.^{81,82} Participants will be provided with a validated automated monitor (Microlife Watch BP Home).⁹⁵ They will be given training and written instructions for HBPM by the recruiting NFP visiting nurse. Participants will be asked to self-monitor their BP 3 times per week, to take 2 readings each time, and to recording readings on a study tracking log provided by the study. NFP visiting nurses will review the log at each visit. During pregnancy and the puerperium, elevated readings (defined as a blood pressure > 140/90 as per the CHAP trial)⁹⁶ will trigger a request from the app for a third reading. If a participant’s third reading is also elevated, the app will trigger a message to the participant to contact their local obstetric provider. After the puerperium and during the postpartum period a blood pressure > 150/100 will trigger a similar alert to their primary care provider. We will follow NFP protocols to establish contact with a primary care provider if the participant does not have one.

Family and maternal demographics. We will collect demographic information at baseline (before study visit 1) and at follow-up (after study visit 3). Participants will be asked to provide information about their pregnancy and household and complete two online packets of questionnaires, which will take about 15 to 20 minutes to complete. Participants will also be given the option to complete surveys on paper if that is their preference.

7.2.1 Visit 1 or Day 1 or Pre-test, etc.

Provide a description of what procedures will be performed on visit 1 or day 1 or pre-test in order of how these will be done. If your study only involves one session or visit, use this section only and indicate 7.2.2 as not applicable.

Study Visit 1 (V1) as summarized in Table 1 will take place at the first home visit after informed consent has been obtained. At this visit, participants will receive “Getting Started” handouts that includes information on setting up the commercially available devices including a 1) a device that monitors physical activity daily for 6 months, 2) a digital scale that monitors weight once per week for 6 months, and 2) a home blood pressure monitor that monitors your blood pressure three times per week for 6 months. NFP visiting nurse will also measure carbon monoxide levels using a provided device at this study visit. During this visit, participants will also be asked to take part in a tobacco cessation program if they have used a nicotine product in the past 3 months. This includes the NFP visiting nurse providing an active referral to a national tobacco quit line and provide a handout on the benefits of and tips for quitting smoking during and or after pregnancy.

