1.0 Objectives

1.1 Study Objectives

Describe the purpose, specific aims or objectives. State the hypotheses to be tested.

Aim 1: To add a cardiovascular health (CVH) module to the existing perinatal home visitation program delivered by Nurse Family Partnership (NFP) visiting nurses in the Northern Appalachian region of Central Pennsylvania.

Aim 2: To train selected NFP visiting nurses on the CVH module and assess the acceptability of the module as well as the fidelity of delivery to pregnant and postpartum women.

Aim 3: To demonstrate the feasibility of enrolling and following pregnant women participating in the NFP program into a pilot research study evaluating a CVH module delivered as part of the existing NFP program.

Aim 4: To develop an activity protocol during and after pregnancy to decrease sedentary behavior during and after pregnancy and increase activity level during the postpartum period.

Aim 5: To pilot the use of digital devices to encourage and monitor activity and associated biometric outcomes, primarily blood pressure and actigraphy.

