8.3 Statistical methods

Describe the statistical methods (or non-statistical methods of analysis) that will be employed.

Descriptive statistics for surveys as well as feasibility (e.g., recruitment and retention, fidelity, data collection methods) and acceptability (e.g., satisfaction) will be calculated.

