13.0 Subject Payment and/or Travel Reimbursements

Describe the amount, type (cash, check, gift card, other) and timing of any subject payment or travel reimbursement. If there is **no** subject payment or travel reimbursement, indicate as not applicable.

Extra or Course Credit: Describe the amount of credit **and** the available alternatives. Alternatives should be equal in time and effort to the amount of course or extra credit offered. It is not acceptable to indicate that the amount of credit is to be determined or at the discretion of the instructor of the course.

Approved Subject Pool: Indicate which approved subject pool will be used; include in response below that course credit will be given and alternatives will be offered as per the approved subject pool procedures.

Participants are eligible to receive up to \$300. Participants will receive \$100.00 after completing the first study visit and baseline survey. Upon completing the second study visit, participants will receive \$100.00. Upon completing the last study visit and follow-up survey, participants will receive \$100.00. Participants will also get to keep the Fitbit and Fitbit Scale they have used during the study.

****Site Congruency: Is the information provided in the above section (Subject Payment and/or Travel Reimbursements) consistent across all relying sites in this research?**

Yes

No - Identify the sites that have dissimilar procedures: *[This field should solely identify the site. Dissimilar procedures across sites should be identified in the SITE workspace via HRP-XXX – R2S Site Plan]*

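### Fidelity has one named source, the delivering nurse's own record, and may be overstated; a few receipt items in the V3 follow-up survey would give a cheap partial cross-check

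*Combined protocol and SAP*

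**What the plan says.** Section 1.1, Aim 2, sets out to train nurses on the module and to "assess the acceptability of the module as well as the fidelity of delivery to pregnant and postpartum women".

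Section 7.2 (Intervention Overview) says who delivers it: "Our pilot CVH intervention will be delivered by NFP visiting nurses". Under Implementation, the same section names the record of delivery: "NFP home visiting nurses will document information related to session implementation (e.g., length of visit, quality of delivery, participant engagement".

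Section 8.3 gives the whole analysis: "Descriptive statistics for surveys as well as feasibility (e.g., recruitment and retention, fidelity, data collection methods) and acceptability (e.g., satisfaction) will be calculated". Fidelity sits under feasibility and satisfaction under acceptability. Neither has a definition or a threshold.

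A participant survey at the end of V1 to V3 is already planned. Section 7.2 (Family and maternal demographics) has participants "complete two online packets of questionnaires, which will take about 15 to 20 minutes to complete", at baseline and after V3, with paper as an option. The Table 1 legend separates survey items from nurse-administered ones ("S=survey; C= client self-monitoring; N= nurse administered") and marks satisfaction as a survey item at V3 only. Section 13.0 ties the final $100 payment to this step: "Upon completing the last study visit and follow-up survey".

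**The concern.** The person who delivers the module is also the only named witness to how it was delivered. When quality of delivery is scored by the deliverer, a high score could mean good delivery or generous scoring, and the data described cannot tell these apart.

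No other source in the protocol fills the gap. Oversight consists of meetings (sections 15.5 and 17.6). The research team does not see the Fitbit or scale data (section 7.2, Digital Device Monitoring). The blood pressure log is filled in by the participant, so it shows self-monitoring rather than delivery of the module.

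What is at stake is how far the fidelity half of Aim 2 can be believed. Section 11.2 says the results will inform a large multi-site trial. If components were missed but recorded as delivered, that trial would be planned on too favourable a picture.

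**Working it through.** The documents give no fidelity rate, target or sample size formula (section 8.2 says none was calculated), so there is no figure to reproduce. The check has three parts. All rates in parts 2 and 3 are assumptions.

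**1. Which recorded items are self-ratings?** Section 7.2 names three examples.
- Visit length is a recorded fact.
- Participant engagement describes the participant.
- Quality of delivery is the nurse's rating of her own work.

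The concern therefore falls mainly on the third item.

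**2. How far could over-recording move the figure?** Let *t* be true fidelity and *s* the share of undelivered content recorded as delivered. Then reported = *t* + (1 − *t*) × *s*.

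| *t* | *s* = 0 | *s* = 25% | *s* = 50% | *s* = 75% |
|---|---|---|---|---|
| 70% | 70% | 77.5% | 85% | 92.5% |
| 80% | 80% | 85% | 90% | 95% |
| 90% | 90% | 92.5% | 95% | 97.5% |

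For example, 0.70 + 0.30 × 0.50 = 0.85. With *s* = 0 there is no distortion, and the documents do not say where *s* lies.

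**3. What could participant receipt items show?** Inputs are 20 women (section 8.1), or 16 responders if 20% are lost (assumed; 20 × 0.8 = 16). Let *q* be the assumed share of women who contradict the nurse record. P(at least one) = 1 − (1 − *q*)^n; for 20 women at 10%, 1 − 0.9^20 = 0.88. P(at least three) is the corresponding binomial tail.

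| Responders | *q* | P(at least 1) | P(at least 3) |
|---|---|---|---|
| 20 | 10% | 0.88 | 0.32 |
| 20 | 20% | 0.99 | 0.79 |
| 16 | 10% | 0.82 | 0.21 |
| 16 | 20% | 0.97 | 0.65 |

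Exact (Clopper-Pearson) 95% intervals for the share reporting receipt are 68% to 99% for 18/20 and 56% to 94% for 16/20. The Quitline item applies to nicotine users, of whom section 3.1 seeks at least 5; 4/5 gives 28% to 99%. Widespread disagreement would probably be seen, but its rate would be poorly estimated.

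**The case against.** The strongest reply is that the instruments are not in these documents. Section 7.0 tells authors to upload data collection materials separately. The satisfaction survey may already ask what was received, and the nurse form, described only by examples, may already be a checklist. This stands: the point is about what the protocol names, and it falls away to that extent if the uploaded forms contain such items.

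Three stronger readings are tempting and not supported.
- A reader might infer that the nurse record is biased upward by a known amount. The documents show neither the direction nor the size; overstatement is a risk only.
- A reader might infer that the primary endpoint of successful integration would be wrongly met. Section 1.2 does not define integration through fidelity and gives no criterion, which is a separate gap that this change leaves open.
- A reader might infer that a participant survey would verify fidelity. It can confirm receipt, but not the quality of delivery or adherence to the scripted content. Disagreement may also reflect poor recall or courtesy towards the nurse, not over-recording.

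Coverage is partial too. The section 7.2 visit text puts V3 about 3 to 4 months after V1, while the intervention may run up to 6 months postpartum. A woman enrolled in the first trimester would reach V3 before delivery, so the postpartum part of Aim 2 would go unchecked for her.

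Finally, this is a descriptive single-arm pilot of 20 women, where self-recording is a defensible choice. That argues for low severity, not for leaving a stated aim with one source when an existing survey can supply a second.

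**Conclusion.** The point holds as a low-severity improvement. The protocol names only the delivering nurses' own documentation as the source for fidelity, so the reported figure, chiefly self-rated quality, may be overstated, and no second source is described.

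The size of any overstatement is unknown. The 70% to 92.5% range rests on an assumed true fidelity of 70% and assumed over-recording of 0% to 75% of undelivered content. The detection probabilities assume that women answer independently and recall correctly. Women who share a nurse may not be independent, so those figures are a guide only.

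The conclusion depends on the uploaded survey and nurse form not already containing equivalent items.

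**What to change.** 1. Check the uploaded survey and nurse form. If they already cover receipt, say so in sections 7.2 and 8.3 and stop there.
2. Otherwise add about five yes/no items to the V3 follow-up survey, completed by the participant without the nurse: handouts received, carbon monoxide reading taken, blood pressure log reviewed, activity goal set, and Quitline referral made (nicotine users only).
3. Have the nurse record the same components on a dated checklist, alongside the quality rating and not in place of it, since that rating is the only quality measure named.
4. In section 8.3, report percent agreement for each item next to nurse-recorded fidelity, descriptively. Give the counts in each direction (nurse yes and woman no, and the reverse), because agreement alone looks high when nearly everything is recorded as delivered.
5. State the limits: receipt only, dependent on recall, nothing after V3, no check of script adherence, and about 20 women (about 5 for Quitline).

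Two passages must be reconciled before the items are worded. Table 1 puts V3 at +2 months, against 3 to 4 months in the visit text. Table 1 also lists nurse-administered carbon monoxide monitoring at all three visits, while the V2 and V3 text does not mention it.

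The cost is five survey items, a small addition to the nurse form, and linkage of the two records by study number. No field staff are needed.
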